#### **15.6 Overview of Plans for Manuscript #2: Medication Adherence during T1 to T2/T3**

Aim 2, Medication Adherence. The analyses concerning adherence will be based on the patient-reported Voils' Medication Adherence Survey (VMAS) at 3 months post-treatment.

Aim 2a. In the combined convenience sample of 1600 participants, two subgroups defined by mental health or substance abuse history (MH/SU Hx: yes, no) will be characterized and compared in terms of medication adherence using the VMAS. We anticipate 50% (n=800) of participants having a MH/SU Hx and 50% (n=800) without a MU/SU Hx. We hypothesize that the two subpopulations are equivalent with regard to medication adherence (<5% difference in medication adherence). Each participant's level of adherence will be classified as high (100% adherent) or low (<100% adherent) for purposes of the analysis. Overall, we anticipate that about 75% of participants will report perfect 100% adherence. Individual adherence may vary depending on treatment regimen, pill burden and patient characteristics. The adherence literature suggests that adherence decreases as the number of pills in the regimen increases (Claxton). The primary characterization of each subgroup, and their comparison, we rely on a logistic regression model for adherence conditional on *subgroup, pill burden, cirrhosis status, age, race, and sex at birth*. The analysis will focus on point estimates and confidence intervals. In particular, the rate (P) of high adherence for each subgroup, and the magnitude of difference between those two rates, are of greatest interest. Of less interest, an equivalence test procedure will be used to test the null hypothesis that the subpopulations do not have equivalent rates. 'Equivalent' will be defined to mean that the difference between population rates, ( $P_1 - P_2$ ), is less than 5%, and thus the null hypothesis is  $|P_1 - P_2| > 5\%$ . For purposes of generating new hypotheses, variations on the model will be explored using additional or alternative covariates such as *marital status, educational status, income level, living situation, employment status, health coverage*, and selected two-way interactions thereof.

Aim 2b. We will investigate the relationship between adherence and pill burden via a logistic regression model for adherence conditional on *pill burden* and the following covariates: *cirrhosis status, age, race, and sex at birth*. The analysis will focus on point- and interval-estimates of the rate of perfect adherence as a function of pill burden evaluated at reference levels of the covariates.

Aim 2c. Descriptive analyses will also be performed investigate prevalence of various reasons patients miss taking medication (i.e., are <100%). The investigation will be based on the responses of those participants who reported imperfect adherence ( $n \approx 400 = 1/4 1600$ ). Each participant will be asked to rate 8 reasons for missing pills, based on a 5 point scale from "not at all" to "very much" We will calculate a score for each reason to determine the most common reasons for nonadherence.

Aim 2d. We will explore the relationship between medication adherence and SVR rate at 3 months post-treatment. The investigation will be based on the combined convenience sample of 1600 participants and will rely on a logistic regression model for SVR that conditions on *adherence group (100% vs < 100% adherent)* and the following covariates: *cirrhosis status, age, race, and sex at birth*. Variations on this model will be explored. The analysis will focus on point- and interval-estimates of the SVR rate as a function of adherence and pill burden evaluated at reference levels of the covariates.

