Antiviral treatment for chronic HCV can permanently eliminate the virus. Patients who successfully complete treatment can achieve a sustained virological response (SVR) or “viral cure” 12 weeks after treatment ends. SVR is associated in some patients with reversal of liver damage, and reductions in liver disease, liver-related death, and death due to all causes (e.g., cardiovascular, diabetes). In addition, SVR is associated with improvements in HRQOL and the symptom of fatigue at 3 months post-treatment. Importantly, many other benefits that may accompany viral cure have not been evaluated.

In the last 3 years, several new DAA medications have been FDA-approved for the treatment of chronic HCV. Other medications for the treatment of HCV are expected to be approved in 2016. Cure rates have typically been between 70% - 90% in phase III drug trials, depending on patient characteristics such as genotype and cirrhosis status. Treatment lasts between 8 and 24 weeks as opposed to previous interferon-based regimens of 24 or 48 weeks. These newly-approved all-oral regimens appear much more tolerable and efficacious in phase III trials, compared to previous interferon-based regimens.

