## 3 STUDY AIMS

### 3.1 Specific Aims

This study is focused on characterizing several HCV treatment regimens in terms of HCV-associated symptoms, treatment side effects, medication adherence, out of pocket costs, and long-term benefits of cure and harms associated with all-oral treatments for chronic hepatitis C, as indicated by the following patient-reported outcomes (PROs) collected before, during and up to one year after HCV treatment:

Aim 1: Evaluate changes from baseline (T1) to during treatment (T2, T3) to characterize harms associated with each treatment regimen (*see manuscript #1 below*) in terms of the following measures:

- 1a. The Memorial Symptom Assessment Scale (MSAS)
- 1b. Specific side effects as measured by multiple PROMIS surveys

- 1c. HCV-specific functional status as measured by the HCV-PRO
- 1d. Pre-existing medical conditions
- 1e. Cumulative out of pocket costs during treatment

Aim 2: Evaluate differences in medication adherence between patients with and without history of mental health/substance abuse (MH/SA Hx) (see *manuscript #2 below*)

- 2a. Characterize and compare the two groups (with and without MH/SA Hx) on medication adherence while accounting for treatment regimen and pill burden.
- 2b. Estimate the effects of pill burden on medication adherence in the combined sample.
- 2c. Estimate the prevalence rates of reasons for nonadherence in the combined sample.
- 2d. Estimate the effect of medication adherence on the SVR rate at 3 months post-treatment.

Aim 3: Evaluate changes from baseline (T1) to 3 months after end of treatment (T4) to characterize short-term benefits of cure in the combined sample of patients (see *manuscript #3 below*)

- 3a: Amelioration of HCV-associated symptoms as measured by the MSAS and PROMIS surveys
- 3b. HCV-functional status as measured by the HCV-PRO

Aim 4: Evaluate changes from baseline (T1) to 1 Year (T5) after end of treatment to characterize long-term benefits or harms (see *manuscript #4 below*)

- 4a. Long-term symptoms as measured with the MSAS
- 4b. Long-term side effects as measured by PROMIS surveys
- 4c. Pre-existing medical conditions
- 4d. HCV-functional status, as measured by the HCV-PRO
- 4e. Differences in 4a-4d between patients with and without cirrhosis

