## 8.2 Procedures for Baseline Collection of Clinical and Lab Data

The RC is responsible for entering the data fields listed in Table 2 in REDCap within one week of the date of consent. The data fields will be extracted from participants' electronic medical records.

Table 2: Clinical and Laboratory Data Collection at Time of Consent	
Clinical and Lab Data	Description
Prescribed Treatment regimen	- sofosbuvir/ledipasvir ( Harvoni ® ) with or without ribavirin - ombitasvir/paritaprevir/ritonavir with dasabuvir ( Viekera Pak ® , VPK ) with or without ribavirin - elbasvir/grazoprevir ( Zepatier ® ) with or without ribavirin - daclatasvir/sofosbuvir, with or without ribavirin ( DAC/SOF ) - sofosbuvir/velpatasvir ( SOF/VEL )
Prescribed Treatment Duration	8, 12, 16, 24 weeks
HCV Genotype 1-6	Confirm genotype 1-6 with most recent lab date
HCV Viral Load	HCV RNA quantitative viral load within last 12 months IU/mL
Evidence of cirrhosis	- No evidence - Yes evidence based on source(s): Fibroscan, biopsy, ultrasound, Fibrosure blood test, clinician judgment
FibroSCAN	kPa stage and grade from Fibroscan results submitted for insurance approval
HIV status	Test conducted and HIV status
Aspartate Aminotransferase	AST IU/L within last 6 months
Alanine Aminotransferase	ALT IU/L within last 6 months
Albumin	ALB g/dL within last 6 months
Total Bilirubin	BILI mg/dL within last 6 months
Creatinine	Creatinine mg/dL within last 6 months
International Normalized Ratio	INR within last 6 months
Platelets	PLAT 10  /uL within last 6 months
Hemoglobin	HGB g/dL within last 6 months

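### The Aim 2d model for SVR leaves out genotype/regimen and pill burden, so its adherence estimate can be confounded and it cannot give the pill-burden results the plan promises

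*Combined protocol and SAP*

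**What the plan says.** Section 3.1 words Aim 2d as an effect: "Estimate the effect of medication adherence on the SVR rate at 3 months post-treatment". Section 15.6 then says the analysis "will rely on a logistic regression model for SVR that conditions on" adherence group (100% versus less) and four further covariates, "cirrhosis status, age, race, and sex at birth". Genotype, regimen and pill burden are not listed. Two sentences qualify this:

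- "Variations on this model will be explored", with no variation named.
- The output is to be point and "interval-estimates of the SVR rate as a function of adherence and pill burden", at reference levels of the covariates.

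Elsewhere the plan says:

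- **Cure.** The Introduction gives phase III cure rates of 70% to 90%, "depending on patient characteristics such as genotype and cirrhosis status".
- **Adherence.** Section 15.6 (Aim 2a) expects that adherence may vary with regimen, pill burden and patient characteristics, and adds: "The adherence literature suggests that adherence decreases as the number of pills in the regimen increases". Section 15.5 (Aim 1e) adds that cost differences between treatments could affect adherence and so SVR.
- **Link.** Table 6 in section 15.12 arranges the regimens under genotype 1 and genotypes 2 and 3.
- **Data.** Table 2 in section 8.2 records the prescribed regimen and its duration, and for genotype: "Confirm genotype 1-6 with most recent lab date".

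**The concern.** A factor that influences both adherence and cure, and is left out of the model, distorts the adherence coefficient. The plan itself describes such a structure. Genotype bears on cure directly. It also largely determines the regimen, and regimen may bear on adherence through pill count or cost. Of the two determinants of cure that the Introduction names, the model keeps cirrhosis and drops genotype. Regimen is a covariate in the models for manuscripts 1, 3 and 4 (sections 15.5, 15.7 and 15.8), and no reason is given for leaving it out here.

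There is also an internal mismatch. A model with no pill-burden term cannot give SVR rates that vary with pill burden. An analyst must either depart from the covariate list or fail to deliver the stated output.

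At stake is how manuscript #2 reads. Some of an apparent benefit of perfect adherence, or some of its apparent absence, could reflect which patients received which regimen.

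**Working it through.** **The plan's own figures.** Expected SVR is 0.94 × 1600 = 1504, which matches the stated 1500 or so and leaves about 100 failures. Expected nonadherent participants are 1600 / 4 = 400, as stated, leaving 1200 adherent. No power or precision is stated for Aim 2d.

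**Question.** If adherence has no effect within genotype strata, what SVR difference appears when the strata are ignored?

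**Inputs.**
- Genotype 2/3 share *w*. The low value is 200/1400 = 14.3%, from the printed rows of Table 6 (120 + 80 = 200 of 960 + 160 + 80 + 80 + 120 = 1400). The high value is 25%, which is what section 15.12 leaves after 60%, 5% and 10% for the three named genotype 1 regimens. The high value is generous, because SOF/VEL may also be used in genotype 1.
- SVR 96% (genotype 1) versus 85% (genotype 2/3). Assumed.
- Nonadherence n₁ versus n₂: 24% versus 28%, up to 20% versus 40%. Assumed.

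**Formulas.** Write s₁ and s₂ for SVR in the two strata.
- N = (1−w)n₁ + w·n₂
- SVR in adherent = [(1−w)(1−n₁)s₁ + w(1−n₂)s₂] / (1−N)
- SVR in nonadherent = [(1−w)n₁s₁ + w·n₂s₂] / N

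**Low case** (w = 1/7, 24% versus 28%). N = 0.2457.
- Adherent: (0.6254 + 0.0874) / 0.7543 = 94.5%
- Nonadherent: (0.1975 + 0.0340) / 0.2457 = 94.2%
- Difference 0.3 points, OR 1.06.

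**High case** (w = 0.25, 20% versus 40%). N = 0.25.
- Adherent: (0.5760 + 0.1275) / 0.75 = 93.8%
- Nonadherent: (0.1440 + 0.0850) / 0.25 = 91.6%
- Difference 2.2 points, OR (0.938/0.062) / (0.916/0.084) = 1.39. Overall adherence is 75% and overall SVR is 0.75 × 96% + 0.25 × 85% = 93.3%, both close to the plan's 75% and 94%.

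**Equal adherence in both strata.** The difference is 0 and the OR is 1.00.

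**Adherence pattern reversed** (w = 0.25, nonadherence 40% versus 20%).
- Adherent: (0.4320 + 0.1700) / 0.65 = 92.6%
- Nonadherent: (0.2880 + 0.0425) / 0.35 = 94.4%
- Difference −1.8 points, so the sign can turn.

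**Yardstick.** The crude 95% half-width for 1200 versus 400 at 93.75% SVR (1500/1600) is 1.96 × √[0.9375 × 0.0625 × (1/400 + 1/1200)] = 2.7 points.

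**Room in the model.** With race as 1 parameter, the listed model has 5 parameters, so 100/5 = 20 failures per parameter. With race as 3 it has 7, so 100/7 = 14.3. Adding genotype (2) and regimen (4) separately gives 100/11 = 9.1 or 100/13 = 7.7. Adding pill burden (1) and a three-level collapsed factor (2) gives 100/8 = 12.5 or 100/10 = 10.

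**The case against.** The strongest reply has four parts.

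1. **The output sentence implies pill burden is fitted.** If so, the pill-count path is largely blocked. That is fair as a guess at intent, but the covariate list says otherwise and the two must be reconciled. Even with pill burden in, genotype and the cost path through regimen stay open.
2. **Aim 2d is exploratory.** Section 15.6 speaks of exploring the relationship and attaches no test or power to it. This stands and limits the weight of the point. But section 3.1 promises an effect estimate, and an unnamed variation is not a planned adjustment.
3. **Bias is not demonstrated.** This also stands. A reader might infer that the estimate is confounded, or that it is inflated. The documents support neither: they say only that adherence may vary, give no rates by genotype or regimen, and leave the sign open.
4. **Separate genotype and regimen terms overlap and cost events.** This stands, and is why a single collapsed factor is the better form.

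Three other stronger readings also fail.

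- Taking SVR as 90% versus 70%, with a 25% share and nonadherence of 20% versus 40%, gives 4.0 points. It implies 85% overall SVR against the plan's 94%, and gives genotype the whole of a range that the Introduction also ties to cirrhosis, which is already in the model. At 85% the half-width is itself 4.0 points.
- Taking 97% versus 76% with a one-in-seven share and the same nonadherence keeps overall SVR at 94% and gives 2.9 points (OR 1.60), just above the half-width. It needs a 21-point gap by genotype, wider than the 20-point span in the Introduction.
- Requiring baseline viral load in the model has no basis here, since nothing in the documents links it to SVR or adherence.

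**Conclusion.** The point holds in limited form. As listed, the Aim 2d model omits a factor that the plan itself connects to cure and, through regimen, possibly to adherence. It also omits a term that its own stated output requires. The adherence estimate can therefore be confounded; the documents do not show that it is.

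Under the assumed rates and no true effect, the spurious difference is 0.3 to 2.2 points (OR 1.06 to 1.39). It is nil if adherence is equal across strata and negative if the adherence pattern reverses. The upper figure is below the crude half-width of about 2.7 points but of similar order. The stratum rates are assumptions, and the calculation uses two strata without the other covariates, so it indicates scale only. The pill-burden mismatch depends on no assumption.

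**What to change.** In section 15.6, Aim 2d:

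- Add pill burden and one collapsed genotype-regimen factor to the SVR model. One possible set of levels is genotype 1 on Harvoni, genotype 1 on another regimen, and other genotypes. Fix the levels before SVR results are examined.
- Fit by penalised (Firth) logistic regression, because only about 100 non-SVR events are expected.
- Keep the current short model as a named sensitivity analysis.
- Describe the result as an association, and align the wording of Aim 2d in section 3.1.

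No new data are needed. Genotype and regimen are in Table 2, and Aims 2a and 2b already need a pill-burden variable. The cost is a somewhat wider interval and fewer events per parameter (from 20 to 12.5, or 14.3 to 10, in the example above). Pill burden may partly overlap with the collapsed factor, since pill count follows from regimen, so the two coefficients should be read with that in mind.

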## 15.7 Overview of Plans for Manuscript #3: Benefits of Achieving SVR

In the combined convenience sample of participants who achieve SVR (estimated to be ~1500), subgroups defined by achievement of SVR will be characterized and compared in terms of changes in PRO measures. The primary analyses for manuscript #3 will rely on a linear model for change from baseline for each PRO variable conditional on covariates which include *SVR status, cirrhosis status, age, race, sex at birth, treatment regimen, subgroup-by-regimen interaction, cirrhosis-by-regimen interaction, and the baseline PRO score*. Including the baseline PRO score as a covariate has several advantages for clarity of interpretation and improved precision of estimators of interest. The analysis will focus on point estimates and confidence intervals. PRO variables of interest in manuscript #3 are described here by aim:

Aim 3a1, MSAS. The outcome variable will be change from baseline (T1) to 3 months after end of treatment (T4). As an aid to interpretation, additional supportive tabulations for each of the 32 symptoms will be examined; e.g., change in side effects or pre-existing symptoms will be characterized in regard to change in raw frequency, severity and distress items.

Aim 3a2, PROMIS®. The primary analyses will focus on 10 symptom-specific PROMIS® T-scores and 1 HIT headache score. The outcome variable will be change from baseline (T1) to 3 months after end of treatment (T4). As an aid to interpretation of the main results, additional supportive tabulations for specific survey items will be examined.

Aim 3b, HCV-PRO. In the primary analysis, the outcome variable will be change from baseline (T1) to 3 months after end of treatment to determine benefit to well-being and functioning after cure (T4).

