### 3.2 Auxiliary Aims

The main objective of this study is to characterize a number of benefits and harms associated with DAA treatment and viral cure as described in Aims 1-4. However, we will also take the opportunity to examine similarities and differences between the treatment regimens using causal inference methods (see *manuscripts #1 and #3 below*.)

Planned Manuscripts to Address Specific Aims 1-4		Analysis
Aim 1: Treatment Side Effects	Manuscript describing PRO changes from baseline to during treatment to characterize each regimen in terms of treatment harms such as side effects (T2/T3 data). Auxiliary analyses will compare regimens.	page 22,25-26
Aim 2: Medication Adherence	Manuscript on medication adherence will compare patients with and without history of mental health/substance abuse, characterize the effects of adherence on SVR rate, explore reasons for nonadherence, and evaluate effects of pill burden on adherence.	page 22,25-26
Aim 3: Benefits of achieving SVR	Manuscript evaluating changes from baseline to 3-months post-treatment (T4) in HCV symptoms and other PROs in patients who achieve SVR to characterize short-term benefits of cure. The main analysis will characterize change in PROs for the total sample and auxiliary analyses will explore differences between regimens.	page 23,25-26
Aim 4: Long-term Benefits/Harms	Report of long-term patient reported harms and benefits associated with HCV treatment at 1 year post-treatment. Evaluate changes in PROs from baseline to T5, and evaluate differences between patients with and without cirrhosis. Auxiliary analyses will explore differences between regimens.	page 23,25-26
PRO Psychometrics	Manuscript to evaluate the psychometric properties of several PROs (HCV-PRO, MSAS, PROMIS) in the HCV population	
Study Protocol	Manuscript describing the PROP UP study design, methodology, and protocol	
Baseline Characteristics	Manuscript describing baseline patient characteristics of the study sample, including HCV-associated symptoms, pre-existing medical conditions, and functional status.	

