#### **15.2 Strategy for analysis of PRO change from baseline as a function of subgroup and/or treatment regimen**

Characterization of each subgroup or treatment regimen in terms of the interval-scale PRO variables will be based on N=1600 participants. Cirrhosis is expected in approximately 50% (n=800) of the subjects. Because subgroups, such as patients with cirrhosis, may have different experiences during and after treatment, estimation and inference characterizing the treatment regimens may be subgroup-specific (e.g., in manuscript #1 and #4). In contrast, primary analysis of the benefits of viral cure (SVR) may be all-inclusive without regard to treatment regimen (e.g., manuscript #2). The general model for change from baseline for each outcome variable (e.g., Total MSAS) may condition on covariates which include *cirrhosis status*, *age*, *race*, *sex at birth*, *treatment regimen*, the *cirrhosis-by-regimen* interaction, and the *baseline score* (e.g., Total MSAS). The models fitted will provide parameter estimates that will be used to obtain point estimates and confidence intervals (CI) to characterize each treatment regimen and/or each subgroup. A limited number of statistical hypotheses will also be tested. For binary PRO scales or subscales, a similar strategy will rely on logistic regression model methods.

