## 15.10 Role of Causal Inference Methods

The participants will comprise two or more regimen-specific treatment cohorts. The auxiliary analyses comparing regimens will require application of causal inference methods.

Two stages of analysis. The causal inference analysis strategy comprises **(1) a design stage** involving estimation and use of a propensity score model for purposes of achieving balance of baseline covariates, and **(2) an outcomes analysis stage** for treatment effect estimation and inference separately for each outcome variable. For these two stages we may rely on the approach proposed by Cao et al. building on previous work by Tan, Robins et al, Funk et al and others. Rotnitzky et al proposed a competing approach and compared the performance of their method to that of Cao et al.. In the manner of Cao et al., we will use an improved doubly robust (DR) estimator obtained via enhancements in the estimation of the propensity score model and the inverse-probability weighted (IPW) outcome model. Confidence intervals will rely on bootstrap methods. Similar analytic methods will be employed to compare patient subgroups or different treatment durations.

Sensitivity Analyses and Diagnostics. Both stages will involve careful use of diagnostic methods (e.g., for covariate balance) and an extensive set of sensitivity analyses. Additionally, to ensure covariate balance in each of the two cirrhosis subgroups, it will be necessary to take steps in the design stage to, for example, appropriately account for subgroup differences in the propensity score model and examine subgroup-specific diagnostics for covariate balance and for propensity score distribution overlap.

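### The auxiliary causal comparison of regimens at T4 has only one model to draw on, and that model conditions on SVR, a result of treatment; its population is stated inconsistently

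*Combined protocol and SAP*

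**What the plan says.** Section 3.2 states that regimens will be compared with causal inference methods and points to manuscripts #1 and #3. Its table adds, for Aim 3: "The main analysis will characterize change in PROs for the total sample and auxiliary analyses will explore differences between regimens". Section 15.10 confirms the method: "The auxiliary analyses comparing regimens will require application of causal inference methods". The design stage described there balances covariates measured at baseline.

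The T4 model is in section 15.7. It opens with "In the combined convenience sample of participants who achieve SVR (estimated to be ~1500"). The same sentence continues that "subgroups defined by achievement of SVR will be characterized and compared in terms of changes in PRO measures", and the covariate list includes "SVR status, cirrhosis status, age, race, sex at birth, treatment regimen, subgroup-by-regimen interaction".

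Other places describe the population differently:

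- Section 3.1, Aim 3: "to characterize short-term benefits of cure in the combined sample of patients".
- Section 3.2, table: "in patients who achieve SVR to characterize short-term benefits of cure", followed by the sentence on the total sample quoted above.
- Section 15.2: "primary analysis of the benefits of viral cure (SVR) may be all-inclusive without regard to treatment regimen". This is tagged to manuscript #2, although the SVR analysis is manuscript #3.

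The auxiliary paragraph at the end of section 15.8 says the causal response models will resemble those for Aims 3a to 3d, but Aim 3 has only parts 3a and 3b.

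**The concern.** A propensity model fitted to baseline covariates aims to make regimens comparable among everyone who started treatment. SVR is observed 12 weeks after treatment ends. If regimens differ in cure rate, selecting on SVR or adjusting for it has two consequences. First, the cured patients on two regimens can differ in unmeasured characteristics that affect both cure and the PRO, and the weighting has not balanced them. Second, the cure pathway from regimen to PRO is blocked, so the contrast is no longer the total effect of the regimen.

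The plan's own text makes the pathway plausible. Section 15.5 says that cost differences between treatments could act on adherence and hence on SVR. The Introduction links SVR to better quality of life and less fatigue at 3 months post-treatment, which is T4. Section 15.4 plans both equivalence and superiority procedures for the regimen comparisons, so removing a real source of difference could favour a finding of equivalence. The plan names no estimand for this contrast and does not say how SVR is to be handled in it.

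**Working it through.** **1. Does the model condition on SVR on every reading?** If the sample is SVR achievers, it does so by restriction. If non-achievers stay in, it does so through the SVR covariate. If the undefined subgroup-by-regimen interaction refers to SVR, the regimen contrast becomes specific to SVR stratum. By contrast, sections 15.5 and 15.8 describe their covariates as baseline ones; only 15.7 adds a post-treatment variable.

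**2. The plan's own sample sizes.** Inputs from section 15.12 and the appendix PROMIS table: SD 10, serial correlation 0.50, two-sided alpha 0.05, 80% power.

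- SD of change = 10 × √(2 × (1 − 0.50)) = 10.
- Harvoni v Zepatier, 960 + 160: SE = 10 × √(1/960 + 1/160) = 0.854. The unequal-variance t-test with the noncentral t distribution gives 2.403; the appendix states 2.40.
- The same method gives 2.918 for 1500 + 100 (stated 2.92) and 3.294 for 960 + 80 (stated 3.29).
- SVR achievers only: 1500/1600 = 93.75%, so 900 + 150 and 900 + 75. The detectable differences become 2.48 and 3.41.

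These rows carry the tag 3A, which I take to mean the auxiliary analyses of manuscript #3. They use full cohorts, so the appendix was not sized for a comparison among achievers only.

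**3. Size of the distortion.** The documents do not give what is needed, so these are assumptions: an unmeasured frailty U ~ N(0,1), left over after the baseline adjustments, that worsens the T4 PROMIS score by 3 points per SD; logit P(SVR) = a − U, with a solved for each cure rate; and uncured patients 5 points worse.

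- Selection part = 3 × (E[U | SVR, regimen A] − E[U | SVR, regimen B]), by Gaussian quadrature.
- Removed part = 5 × (SVR rate A − SVR rate B).

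| SVR A v B | E[U given SVR], A | E[U given SVR], B | Selection | Removed | Total |
|---|---|---|---|---|---|
| 95% v 93% | −0.0471 | −0.0649 | 0.05 | 0.10 | 0.15 |
| 94% v 90% | −0.0560 | −0.0908 | 0.10 | 0.20 | 0.30 |
| 96% v 92% | −0.0380 | −0.0736 | 0.11 | 0.20 | 0.31 |
| 96% v 88% | −0.0380 | −0.1077 | 0.21 | 0.40 | 0.61 |
| 94% v 94% | −0.0560 | −0.0560 | 0 | 0 | 0 |

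If everyone stays in and SVR is a covariate (equal arms, no interaction), the selection part is 0.11 for 96% v 92% and 0.22 for 96% v 88%, and the cure pathway is still removed. The choice between the two readings therefore does not matter much.

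**4. Sensitivity.** With the frailty log-odds halved, the selection part for 96% v 92% falls from 0.11 to 0.06. A latent-normal model, with correlations of 0.3 to 0.7 between frailty and cure and 0.3 to 0.5 between frailty and outcome, and an SVR effect of 3 to 6 points, gives:

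- 94% v 90%: selection 0.06 to 0.24, removed 0.12 to 0.24, total 0.18 to 0.48.
- 94% v 85%: selection 0.13 to 0.52, removed 0.27 to 0.54, total 0.40 to 1.06.

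**The case against.** The strongest reply is that the population is not fixed by the text. A reader might infer from the opening of section 15.7 that the T4 regimen comparisons are made only among patients who achieved SVR. The documents do not support that. The same sentence compares SVR groups, the model contains SVR status, sections 3.1, 3.2 and 15.2 speak of a combined, total or all-inclusive sample, and the 3A rows use full cohorts. Section 15.7 does not itself describe a weighted regimen comparison. This reply stands, but it does not remove the problem, because the other reading adjusts for SVR.

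The reference to Aims 3a to 3d in section 15.8 may be a slip for 4a to 4d, whose model has no SVR term. That is plausible. It would leave the manuscript #3 comparison promised in section 3.2 with no model except that of 15.7.

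Conditioning on cure suits the main descriptive question of Aim 3, which is change after cure. That also stands, and the point does not touch that analysis. Regimen comparison is auxiliary and, by the plan's own account, not the purpose of the study.

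Two stronger claims about size and direction are tempting. Taking the 70% to 90% cure range in the Introduction as a regimen contrast would give about 1.5 points (0.49 + 1.0). But that range is said to vary with patient characteristics such as genotype and cirrhosis, and no mixture of 70% and 90% can average the anticipated 94%. A reader might also infer that the distortion always favours the regimen with the lower cure rate. That follows only from the assumed signs. The outcome is change from baseline, and if frailer patients have more room to improve, the selection part reverses.

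Section 15.10 does plan to explore residual bias from unmeasured confounders, but it says nothing about conditioning on a post-treatment result.

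**Conclusion.** The point holds in a limited form. The plan promises a causal regimen comparison in manuscript #3, and the only T4 model it supplies conditions on SVR, by restriction or by adjustment. Weighting on baseline covariates does not protect such a contrast, and the contrast leaves out any effect that acts through cure. With cure rates near the anticipated 94% and gaps of about 4 percentage points, the distortion is about 0.3 PROMIS point. An 8-point gap gives about 0.6. Both are well below the 3-point important difference and the 2.40 points detectable with 960 + 160. These sizes rest on assumed frailty and non-cure effects that the documents do not provide. The distortion requires regimens to differ in cure rate and, for the selection part, an unadjusted common cause of cure and PRO. It is worth correcting because the remedy is specific and nearly free, not because it threatens the main aims.

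**What to change.** - In sections 15.7 and 15.10, state that causal regimen comparisons at T4 include every participant who started treatment, whatever the SVR result, with no SVR term in the regimen outcome model.
- Correct the Aim reference in the auxiliary paragraph of section 15.8 so that it names models that exist and makes clear whether they contain SVR.
- Reconcile the population of manuscript #3 across sections 3.1, 3.2, 15.2 and 15.7. The analysis in SVR achievers can remain for the main descriptive aim.
- Label any regimen contrast within SVR achievers as descriptive. If it is to be read causally, define it as a principal-stratum estimand and state its assumptions.

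The cost is SAP wording. About 100 more participants (1600 − 1500) enter the comparison. Their T4 surveys are already scheduled, and section 4.3.3 encourages those who stop therapy early to complete the remaining assessments. Precision is not reduced: the PROMIS detectable difference for 960 + 160 stays at 2.40, against about 2.48 if restricted to SVR achievers.
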